8.4 Precautions and Warnings, Prohibited Medications/Treatments and Restrictions

8.4.1 Precautions and Warnings

- The device must not be used if the expiry date has lapsed, if the packaging or contents are damaged, or if the gel in the syringe appears inhomogenous and/or cloudy
- The device should not be injected into blood vessels, bones, tendons, ligaments, nerves, muscles or naevi
- Immediately stop the injection if a subject exhibits any signs or symptoms associated with injection into a blood vessel, such as changes in vision, signs of a stroke (including sudden difficulty speaking, numbness or weakness in their face, arms or legs, difficulty walking, face drooping, severe headache, dizziness, or confusion), white appearance (or blanching) of the skin, or unusual pain during or shortly after the procedure
- In case of a vascular event, emergency treatment must be sought, and high dose hyaluronidase (Alam et al., 2008), vigorous massage and heat (gauze with hot water) should be applied. In addition, topical 2% nitroglycerin paste may encourage vasodilatation (Belazay et al., 2015)
- The device should never be placed in contact with quaternary ammonium compounds (such as benzalkonium chloride solutions) or with medical-surgical instruments that have been in contact with these substances

Upon completion of device administration

- After injection the investigator may apply a light massage for uniform distribution of the filler
- Application of ice packs for 5-10 min. post injection is optional and may reduce redness
 and swelling; this have to be recorded in the clinical investigation eCRF(s) along with any
 other concomitant medication/treatment
- The subject should be requested to stay in the office for a period of at least 30 minutes after the injection to assess pain following injection and to detect possible blanching caused by arterial occlusions

- The health care professionals must be familiar with the signs and symptoms associated with vascular occlusion, and have a plan detailing how to treat the subject in the event of vascular occlusion; this may include on-site treatment and/or immediate referral to another health care professional for treatment. For instance, in the event of blindness or any ophthalmic signs or symptoms, subjects have to undergo immediate evaluation by a ophthalmology specialist. Ophthalmology specialists (ideally a Retinal Specialist, if readily available) near each investigational site who are able to immediately examine subjects should be identified and informed about the clinical investigation procedure. Additionally, a specific treatment protocol in case of unintended intravascular injection that is consistent with those recognized by national, professional societies should be in place at each investigational site.
- The following information will be recorded in the eCRF(s) for each of the treatments administered: date of application, the side of application, injection technique, exact start time and end time of injection, injected volume of the device (see Section 8.3.4) and device ID.

8.4.2 Prohibited Medications/Treatments

The following medications/treatments will be prohibited:

- From ten days before Day 0 (Baseline) until three days post-injection: use of anticoagulant, antiplatelet or thrombolytic medication
- Current treatment with immunomodulating therapy

8.4.3 Restrictions

- Subjects must be advised not to apply any make-up for twelve hours after the injection
- Subjects should avoid prolonged exposure to sunlight and ultraviolet (UV) for one week after injection
- Subjects should abstain from use of saunas or Turkish baths for one week after the injection
- Subjects should abstain from frequent solarium visits
- Subjects should abstain from consuming alcohol, nicotine –containing products one hour before and after injection

- Subjects should not massage the treatment site or apply pressure to the area for one week following the injection, to avoid the possible risk of device mobility
- Subjects should avoid strenuous exercise within 24 hours after injection

8.5 Rescue Medication

In case of overcorrection, commercially available hyaluronidase should be used at the discretion of the treating investigator, in accordance with the American Society for Dermatologic Surgery guidelines (Alam et al., 2008).

If the subject complains of ocular pain or vision changes, they should be immediatey refered to an ophthamolgy specialist.

8.6 Medical Device Accountability

The assumed average volume of such device to be administred for this indication is 2.0 mL per fold for the initial treatment, 1.0 mL per fold for potential additional touch-up treatment and 2.0 mL per fold for potential repeat treatment. Considering the number of subjects to be enrolled (270 subjects), it is anticipated that maximum of 1,860 units of Princess® FILLER Lidocaine, as well as the 900 units of the control device, will be used during this clinical investigation.

The clinical investigation material must not be used outside the context of this CIP. Documentation of receipt, dispensing and return of all IMDs must be performed by the principal investigator or his/her designee. It is the principal investigator's responsibility to ensure that all clinical investigation materials are kept in a secure location, with access limited to individuals authorized by the principal investigator. At the end of the investigation, all remaining clinical investigation material should be destroyed on site, following the site-specific destruction procedure after a monitor has verified all accountability documentation. If the site does not have an appropriate destruction process, the material must be returned to the sponsor designee. Records on investigational device delivery to the center, the inventory at the site, the use by each subject, and return to the sponsor must be maintained by the principal investigator or designee. Forms will be provided to enhance device accountability.

As the preparations are for use of the treating investigator only, compliance will be controlled by the drug accountability log and empty packages only. Empty or used syringes will not be returned to the sponsor, but will be destroyed as per investigational sites's procedures.

9 Subject Selection, Withdrawal and Discontinuation

9.1 Inclusion and Exclusion Criteria – Screening/Baseline

9.1.1 Inclusion Criteria

Subjects who meet ALL the following criteria are eligible for this clinical investigation:

- 1. Male or female subjects, 22 years of age or older, at the Screening visit
- 2. Subjects with two fully visible, approximately symmetrical moderate to severe NLFs (same severity) with severity scores of 2 or 3 on the 5- point NLF-SRS for both NLF as judged by the treating investigator in conjunction with the independent blinded evaluating investigator.
- 3. Females of childbearing potential must have a negative urine pregnancy test at injection visits and must agree to use an adequate method of contraception for the duration of the clinical investigation
- 4. Healthy skin in the nasolabial area and free of diseases that could interfere in cutaneous aging evaluation
 - 5. Willingness to abstain from any aesthetic or surgical procedures in the treatment area for the duration of the clinical investigation, including botulinum toxin injections (except glabellar or forehead botulinum toxin treatment)
- 6. Subjects having understood the purpose and conduct of the clinical investigation and having given written informed consent

9.1.2 Exclusion Criteria

Subjects who meet **ANY** of the following criteria are **NOT** eligible for this clinical investigation:

- 1. For females: pregnant and/or lactating or planning to become pregnant during the clinical investigation
- 2. History of allergies or hypersensitivity to HA preparations, lidocaine or anesthetics of any amide-based anesthetic

- 3. Since Juvéderm® Ultra XC contains trace amounts of Gram-positive bacterial proteins, subjects with history of allergies to such material can not be included in this clinical investigation
- 4. Tendency to keloid formation, hypertrophic scars and/or pigmentation disorders
- 5. Known human immune deficiency virus-positive individuals
- 6. Presence of infectious, inflammatory or proliferative cancerous or pre-cancerous lesions in the area to be treated
- 7. Re-current herpes simplex in the treatment area
- 8. History or presence of any autoimmune or connective tissue disease, or current treatment with immunomodulating therapy
- 9. Uncontrolled (or instable) diabetes mellitus or systemic diseases
- 10. Facial plastic surgery, tissue augmentation with silicone, fat or another non-absorbable substance (permanent fillers) area of device application
- 11. Implantation of facial dermal fillers in the treatment area in the preceding twelve months
- 12. Skin of the nasolabial region affected by aesthetic treatments (e.g. laser therapy, absorbable and non-absorbable sutures (threads), microneedling and/or botulinum toxin within the last twelve months, dermabrasion and mesotherapy within the last six months, chemical peeling within the last three months) or planning to undergo such procedures during the clinical investigation
- 13. Facial lypolysis, including submental fat treatments, within last month prior to enrollment and during the clinical investigation
- 14. Bariatric surgery within 12 months prior to enrollement and during the clinical investigation
- 15. History of bleeding disorders and/or use of anticoagulant, antiplatelet or thrombolytic medication from ten days pre- to three days post injection
- 16. Planned dental/oral surgery or modification (bridge-work, implants) within two weeks prior injection and to a minimum of four weeks post injection
- 17. Any medical condition prohibiting the inclusion in the clinical investigation according to the judgment of the treating investigator
- 18. Previous enrollment in this clinical investigation

- 19. Current participation in another clinical investigation, or treatment with any investigational drug/medical device within 30 days prior to clinical investigation enrollment
- 20. Any dependency of the subject to the treating investigator, the blinded independent evaluating investigator or clinical investigation site (e.g. employees of the sponsor), or subjects who are employees or relatives of the treating investigator and/or the independent blinded evaluating investigator
- 21. Subjects who have one of the following assessments during the visual examinations at Baseline: Snellen visual acuity test worse than 20/40 (with corrective eyewear, if applicable), abnormal confrontational visual field test, or abnormal ocular motility test.

9.2 Inclusion and Exclusion Criteria – Repeat-treatment

9.2.1 Inclusion Criteria

Subjects who meet ALL the following criteria are eligible for a repeat-treatment:

- 1. In the opinion of the treating investigator, the subject has returned to sufficient severity of both NLFs that would have qualified him for enrollment into the clinical investigation initially (note that the subject does not have to return to his Baseline severity to be permitted to receive a repeat treatment)
- 2. Subjects with NLFs with severity scores of 2 or 3 on the 5-point NLF-SRS for both NLFs as judged by the treating investigator in conjunction with the independent blinded evaluating investigator (note that it is not necessary for the treating and evaluating investigator to agree on the same rating)
- 3. Females of childbearing age must have a negative urine pregnancy test at the repeat-treatment visit and must agree to continue to use an adequate method of contraception for the duration of the clinical investigation
- 4. Healthy skin in the nasolabial area and free of diseases that could interfere in cutaneous aging evaluation and/or injection

9.2.2 Exclusion Criteria

Subjects who meet **ANY** of the following criteria are **NOT** eligible for a repeat-treatment:

- CPH-301-201200F
- Occurrence of an SAE or adverse event of special interest (AESI; i.e., changes in vision [loss
 of vision, blurriness, double vision, pain in or around the eye, blindness, blind spots,
 problems moving the eyes, change in peripheral vision], skin changing color around the
 eyelids or around the site of injection) during or after the initial injection and/or touch-up
 injection
- 2. Subjects who experienced visual changes or other serious medical conditions during or after the initial/touch-up injection
- 3. Subjects who have one of the following assessments during the visual examinations:
 - Snellen acuity test worse than 20/40 (with corrective eyewear, if applicable)
 - abnormal confrontational visual field test
 - abnormal ocular motility test
- 4. Subjects who became pregnant since start of the study or are planning to become pregnant during the clinical investigation
- 5. Known human immune deficiency virus-positive individuals
- 6. Presence of infectious, inflammatory or proliferative cancerous or pre-cancerous lesions in the area to be treated
- 7. Development of recurrent herpes simplex in the treatment area since study start
- 8. Development of any autoimmune or connective tissue disease since start of participation in the study, or current treatment with immunomodulating therapy
- 9. Development of uncontrolled (or instable) diabetes mellitus or any other systemic disease since study start
- 10. Development of a bleeding disorder since study start or use of anticoagulant, antiplatelet or thrombolytic medication from ten days pre- to three days post injection
- 11. Planned dental/oral surgery or modification (bridge-work, implants) within 2 weeks prior to injection and to a minimum of four weeks post injection
- 12. Any medical condition prohibiting the inclusion for repeat treatment according to the judgement of the treating investigator

9.3

Subject Withdrawal and Discontinuation

Each subject has the right to withdraw his/her consent to participate in the clinical investigation at any time and without giving reasons.

Subjects may be discontinued for the following reasons:

- Lost to Follow-Up
- Consent withdrawal (the treating investigator must try to find out and document the reasons for withdrawal of consent)
- Safety reasons including abnormal and clinically significant changes in visual examinations (see Section 10.8.4)
- Treating investigator's decision
- Poor compliance and/or disregard of the treating investigator's instructions
- Major CIP violation

In case of early withdrawal, reasons, circumstances and findings should be described as completely as possible on the "Early Termination" page in the CRF respecting the subject's privacy. Subjects who are withdrawn prematurely should undergo an early termination visit with the assessments that are scheduled for Week 40 (Visit 8a) or Week 52 (Visit 8b) or Visit 8c.

In accordance with similar studies in this indication, the expected lost to follow-up rate is estimated to reach approximately 5% and repeat treatments will be offered in this clinical investigation to further decrease the amount of lost to follow-up subjects. Due to the split face design, minimal attrition bias is expected.

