7.6 Randomization and Blinding

Randomization will be performed at Baseline (Visit 2) per clinical investigation site via interactive web response system (IWRS). Each participant will receive Princess® FILLER Lidocaine in one NLF and Juvéderm® Ultra XC in the contralateral NLF, with allocation of respective fillers to the sides randomized as followed:

• Group A:

- > Princess® FILLER Lidocaine on left NLF
- ➤ Juvéderm® Ultra XC on right NLF

• Group B:

- ➤ Juvéderm® Ultra XC on left NLF
- > Princess® FILLER Lidocaine on right NLF

The treating investigator performing the treatment will be aware of the device injected (unblinded treating investigator).

The independent blinded evaluating investigator will not be aware of the device injected. To check if the independent blinded evaluating investigator has been successfully blinded, the following questions will be asked after the initial treatment:

- Can you guess which of the two fillers the subject has received into the left nasolabial fold?
- If Yes, which one?
- Why do you deem that the subject has received that filler into the left nasolabial fold?

 The subject will be blinded using a blindfold. To check if the subject has been successfully blinded, the following questions will be asked after the initial treatment:
- Can you guess which of the two fillers you've received into the left nasolabial fold?
- If Yes, which one?
- Why do you deem that you've received that filler into the left nasolabial fold?

Moreover, an evaluation of NLFs severity by three independent blinded photographic reviewers using the 5-point NLF-SRS and based on photographs will take place at the end of the clinical investigation. Each of the three independent blinded photographic reviewers will review all photographs. These independent blinded photographic reviewers, will not be aware of the treatment allocation. They will be dislocated from the clinical investigational sites, will have

no access to randomization schedule, and will not discuss any findings with the treating investigators or independent blinded evaluating investigators during the clinical investigation and until the final database lock.

The repeat-treatment will be performed with Princess® FILLER Lidocaine on both NLFs.

The randomization assignment should not be revealed before the database has been cleaned and closed.

Emergency unblinding

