5.1. Primary Effectiveness Endpoint

The estimand for the primary effectiveness endpoint is defined as follows:

- Treatment: Princess® FILLER Lidocaine and Juvéderm® Ultra XC for the treatment of NLF (both sides) in each subject.
- Population: Of all subjects defined by the study inclusion / exclusion criteria, the analysis population will include subjects who were randomized to the study treatment and received both treatments (Princess® FILLER Lidocaine and the control medical device) as initial treatment at the same visit (FAS population).
- Variable: A binary variable indicating the subject is alive and has a NLF-SRS response based on the independent blinded evaluating investigator live assessment using the NLF-SRS at Week 24 after initial treatment and relative to baseline assessments. NLF-SRS responder with regards to each specific NLF is defined as a subject with at least one grade improvement from baseline in NLF-SRS in that NLF.
- Intercurrent events:
 - The intercurrent event 'death' is very unlikely in this study, however, in case of death prior to Week 24, this will be considered as non-response following the composite strategy.
 - Major protocol deviations impacting the NLF-SRS assessment will be handled using the treatment-policy strategy, i.e., the NLF-SRS value at Week 24 will be used for categorization of response.
- Population-level summary: Paired difference of NLF-SRS response rates between Princess® FILLER Lidocaine and the control medical device for non-inferiority comparison.

Study discontinuation (due to any reason) prior to Week 24 is not considered as an intercurrent event, however this will lead to missing Week 24 values, which will be imputed using single imputation strategy as non-response for the primary analysis of this estimand. Subjects with missing NLF-SRS value at Baseline will be considered as non-response for the primary analysis of this estimand.

5.2. Key Secondary Effectiveness Endpoint 1

The estimand for the key secondary effectiveness endpoint 1 is defined as follows:

- Treatment: Princess® FILLER Lidocaine and Juvéderm® Ultra XC for the treatment of NLF (both sides) in each subject.
- Population: Of all subjects defined by the study inclusion / exclusion criteria, the analysis population will include subjects who were randomized to the study treatment and received both treatments (Princess® FILLER Lidocaine and the control medical device) as initial treatment at the same visit (FAS population).

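### Protocol 9.3 permits ending follow-up before Week 24 for non-safety reasons; the missing grade is then scored as non-response on both folds, which is not conservative for non-inferiority

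*Protocol*

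**What the plan says.** Protocol 9.3 opens its list with "Subjects may be discontinued for the following reasons". Beside loss to follow-up, consent withdrawal and safety, the list contains "Treating investigator's decision" (no criteria given), "Poor compliance and/or disregard of the treating investigator's instructions" and "Major CIP violation". Protocol 7.6 adds: "The treating investigator performing the treatment will be aware of the device injected".

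SAP 5.1 has two rules that meet here:

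- For deviations: "Major protocol deviations impacting the NLF-SRS assessment will be handled using the treatment-policy strategy". The Week 24 grade is to decide response.
- For discontinuation: "Study discontinuation (due to any reason) prior to Week 24 is not considered as an intercurrent event". The Week 24 value is then missing and is imputed as non-response. SAP 6.3 expects both folds to be missing together.

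The early termination visit is described twice. Protocol 9.3 points to the Visit 8 assessments; 10.12 points to the end-of-investigation visit at Week 48, Week 60 or Visit 9c. The visit lists in 10.11.12 and 10.11.13 do not include NLF-SRS. SAP 6.4 derives no visit windows, so no other grade would be carried to Week 24.

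Protocol 14.2 and SAP 6.3 call the non-response imputation conservative.

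**The concern.** The estimand relies on a grade that 9.3 allows a site not to collect. A major deviator who stays is graded and analysed as observed. One who is discontinued before Week 24 becomes a pair of non-responses in the FAS. SAP 4.5 names premature termination as a possible major deviation, so that subject may also leave the PPS.

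Protocol 9.3 expects little attrition bias because the design is split-face. Both folds do leave together, but a face where only one fold responded carries one-sided evidence, and that evidence goes with it. One of the three reasons is a decision by the unblinded injector, who also grades both folds live (10.1). Loss could therefore depend on how one side is doing. Study injections before Week 24 end with the Week 2 touch-up, so ending follow-up for these reasons loses effectiveness data without any gain for the Week 24 comparison.

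**Working it through.** **Inputs.** Randomized n = 270 (Protocol 9.4). Margin -10 points; assumed response rates 88% and 87% (14.3). One-sided alpha 0.025 (SAP 8.2.1); the protocol has one-sided 0.05. Assumed here, because the documents give no figure: k = 3 or 5 faces discontinued for these reasons (1.1% to 1.9% of 270).

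**The plan's own figure.** Discordance is 0.88 x 0.13 + 0.87 x 0.12 = 0.2188. At n = 222 and one-sided 0.05, simulated power is 88.5-88.7%, against the stated 90%. That plan used 1600 simulations, with a standard error of sqrt(0.9 x 0.1/1600) = 0.75 points, so the paired set-up reproduces adequately.

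**Test used.** Let b be the number of faces where only Princess responds and c the number where only Juvéderm responds:

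- D = (b - c)/n
- lower limit = D - z x sqrt{[(b + c)/n - D²]/n}

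Non-inferiority is concluded if the limit exceeds -10 points.

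**At the margin (78% against 88%).** With independent folds, b is 0.78 x 0.12 = 9.36% and c is 0.88 x 0.22 = 19.36%. With correlated folds at 16% discordance, b is 3% and c is 13%.

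**What one rescored face does.**

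- Only Juvéderm responded: D moves by +1/270 = +0.37 points.
- Only Princess responded: -0.37 points.
- Both or neither responded: 0.
- Average if loss is unrelated to side: (c share - b share) x 0.37 = 0.10 x 0.37 = +0.04 points, in either correlation case.

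So 3 to 5 faces move D by about 0.11 to 0.19 points if loss ignores side, and by 1.11 to 1.85 points if every lost face is a Princess-only failure.

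**False non-inferiority in the FAS** (simulation, one-sided 0.025):

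| Folds | No loss | 3-5 faces, unrelated to side | 3-5 faces, all Princess-only failures |
|---|---|---|---|
| Independent | about 2.7% | 2.8-3.1% | 6.0-9.7% |
| 16% discordance | 3.2% | 3.5-3.7% | 9.2-16.3% |

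At the protocol's one-sided 0.05, the extreme column with independent folds starts at 5.2% and becomes 10.5% and 15.9%.

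**If the faces are dropped instead, as in the PPS.** When loss is unrelated to side, the rate stays at about 2.6% (independent folds). In the extreme case it is 5.5% and 8.6% (independent) or 8.2% and 14.3% (16% discordance). Requiring both sets therefore protects against side-blind loss if these subjects are in fact dropped from the PPS, but only slightly against side-related loss.

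**On the conservative label.** The plan argues that lower response rates make non-inferiority harder to show. A 0/0 pair lowers both rates equally, so its own difference is zero while the denominator stays at 270. If a share m of faces is scored this way regardless of side, a true -10 is expected to show as -10(1 - m).

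**The case against.** - **Discontinuation is optional.** A reader might infer that a violation always costs the Week 24 grade. The text of 9.3 is permissive. A violator who stays is graded as the estimand says, and only subjects discontinued before Week 24 are affected.
- **SAP 5.1 does not contradict itself.** It separates a deviation with a value from a discontinuation without one. The gap is that 9.3 lets a site move a subject from the first case to the second.
- **Selective removal is not shown.** A reader might infer that the injector will remove faces unfavourable to Princess. No passage supports that. Only one of the three reasons is the injector's own decision, the major/minor classification is made at a blinded review (SAP 4.5), and withdrawal reasons are tabulated and listed (SAP 7.1). The 6.0-9.7% and 9.2-16.3% figures are an upper extreme.
- **Planned analyses address it.** The worst-case analysis scores missing Princess as failure and missing Juvéderm as response, which is the true value of a Princess-only failure. For loss unrelated to side it is stricter than needed: 0.6% false non-inferiority at k = 5, independent folds. Multiple imputation and tipping point analyses are also planned. It would be wrong to say that the plan has no protection. But the decision rests on the FAS and PPS analyses, and none of these analyses recovers the grade.
- **The 10% allowance is not a discontinuation rate.** It covers PPS exclusions for major deviations or loss to follow-up, and many such subjects may have a Week 24 grade.
- **Early termination at Week 48.** The wording in 10.12 might be read as Visit 7, which does include NLF-SRS. Even so, the grade would belong to the early termination visit and nothing maps it to Week 24.

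These points reduce the size and remove any suggestion of intent. The gap in data collection stands.

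**Conclusion.** The point holds as a modest, cheaply corrected weakness. For subjects discontinued before Week 24 under the three non-safety reasons, the treatment-policy handling in SAP 5.1 cannot be applied, and the replacement score favours non-inferiority instead of guarding against it.

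If such loss is unrelated to side, the FAS effect for 3 to 5 faces is small, at most about half a percentage point of false non-inferiority. It becomes material only if loss is related to side, and the upper figures require every lost face to be a Princess-only failure. All figures rest on the assumed 3 to 5 faces, n = 270, a true difference exactly at the margin and one-sided 0.025. The actual number of these discontinuations cannot be inferred from the documents.

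**What to change.** In Protocol 9.3, for a major CIP violation, poor compliance and a treating investigator's decision made on non-safety grounds, separate stopping study treatment from ending follow-up. Ask subjects who still consent to attend the scheduled Week 12 and Week 24 visits for NLF-SRS, photographs and GAIS, and flag them as deviators. Their Week 24 grade can then be used in the FAS as SAP 5.1 intends.

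Leave the rules for consent withdrawal, loss to follow-up and safety withdrawal (9.3, 10.8.4) as they are. Reconcile the early termination visit contents in 9.3 and 10.12, which name different visits. In Protocol 14.2 and SAP 6.3, drop or qualify the statement that non-response imputation is conservative.

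The cost is protocol and SAP wording, plus sites following a few non-compliant subjects through visits that are already scheduled.
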